11.2.5 Demographic and Baseline Characteristics

The number of patients enrolled into the study (both Phase 1 and Phase 2) will be summarized by CTP sites and overall. Treatment groups will be described in terms of demographics and baseline diagnostic and clinical characteristics. The description of categorical and ordinal variables will be in terms of proportions; the description of continuous variables will be in terms of means and standard deviations, medians, quartiles, and minimum and maximum values. Variables found to be different between the groups at baseline will NOT be automatically included in the analyses; the effect of such imbalance on the inferences about the study hypotheses will be assessed only as an exploratory analysis.

To assess the prognostic power and potentially differential effect of gender and ethnicity on treatment outcome, the hypotheses and all exploratory questions will be repeated adjusting for these factors, including both main effects and interactions (with treatment) terms.

11.2.6 Adjusting for Covariates

There are no known factors that affect treatment outcome both in Phase 1 and Phase 2. Therefore the primary analysis of the study hypotheses will be performed without adjusting for any covariates. Secondary analysis will be performed adjusting for the a priori identified covariates. Adjusting for factors found to differ between treatment groups at randomization is a data-driven analysis and will be considered exploratory.

11.2.7 Modeling of Site Effects

The outcomes of subjects from the same site are expected to be correlated. To account for these correlations in the analysis, all tests will be based on Generalized Estimating Equations (GEE) models [Diggle, PJ, Liang K-Y, and Zeger, SL (1994) Analysis of Longitudinal Data, Oxford University Press, Oxford]. GEE approach allows modeling of correlated data that is not necessarily normal, such as the primary outcomes for both Phase 1 and Phase 2. This method is generally robust with respect to misspecification of the correlation structure of the outcome in the sense that it produces unbiased estimates of the parameters in the model for the mean.

The goal of this study is to estimate an overall effect of EMM vs. SMM, rather than to study efficacy in individual sites. There is no evidence that the relative efficacy will differ between sites or that overall efficacy of EMM and SMM will be different in different sites, either for Phase 1 or for Phase 2 study. Therefore, main effects for sites and interaction between sites and treatment will be investigated only as an exploratory analysis.

The GEE approach also allows specification of more than one clustering factor. In this study, in addition to site, repeated measurements over time would constitute another clustering factor. GEE will be used to account for the correlation due to repeated measurements over time and the correlation due to correlation within site.

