5.2 Community Treatment Programs (CTPs)

5.2.1 Number of CTP Sites

It is estimated that 12 CTP sites will participate in this study.

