11.2 General Analytic Strategy

11.2.1 Significance Testing

All hypotheses will be tested by two-sided tests with level of significance $\alpha=0.05$. All exploratory analyses will be reported as such and will be thoroughly described in any publication. In particular, the modeling strategy for identification of predictors of outcome (such as inclusion of multiple covariates and interactions) will be explained in detail to allow adequate assessment of the strength of inferences based on data-driven statistical models.

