11.2.4 Missing Data and Dropouts

Every possible effort will be made to assess all patients in both Phase 1 and Phase 2. Despite our thorough and proactive approach to taking complete measurements on all randomized study patients at all time points, it is expected that there will be cases when assessments will be incomplete or missing.

Accounting for dropout in the analysis. The primary qualitative outcome measures, success/failure in Phase 1 and substantial improvement (yes/no) in Phase 2 will be determined for all study patients, regardless of whether they completed the treatment in these phases or not (see *Treatment Success/Failure for Dropout and Missing Data* on page 11-7 and *Substantial Improvement Status for Dropout and Missing data* on page 11-10). The analysis of the quantitative outcomes, measuring severity of symptoms and positive/negative weekly urines will be based on generalized linear models and Generalized Estimating Equations (GEE) models [Diggle, PJ, Liang K-Y, and Zeger, SL (1994) *Analysis of Longitudinal Data*, Oxford University Press, Oxford]. The GEE methodology requires no parametric distribution assumption, provides robust inference with respect to misspecification of the covariance, and allows analysis of continuous, categorical, and count data which may be missing for some patients either because of a missed week or due to drop-out. Thus, complete information for all patients is not needed. PROC GENMOD in SAS (2003) will be used to carry out these analyses.

The inferences from incomplete or missing data are valid provided that the missing data are missing at random (Little and Rubin, 1987). “Missing at random” means that the missing mechanism does not depend on the value of the unobserved outcome. Unfortunately, this assumption is untestable in most medical research, as in this study.

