11.3.4 Hypotheses Testing

Primary Hypothesis 1.1. There will be a higher rate of treatment success among subjects receiving EMM than among patients receiving BUP/NX and SMM alone.

The following model will be used to test this hypothesis:

(1)

$$(2) \quad \text{logit}(Y_{ij}) = \beta_0 + \beta_1 \text{txt}_{ij} ,$$

where Y_{ij} is a dichotomous measure indicating whether the j^{th} patient of the i^{th} site meets the Phase 1 criteria for success or not, with $Y_{ij}=1$ for success and $Y_{ij}=0$ for failure; txt_{ij} is an indicator variable for treatments, with $\text{txt}_{ij}=1$ for EMM group and $\text{txt}_{ij}=0$ for SMM group. The model parameters will be estimated by GEE (see *Modeling of Site Effects* on page 11-4). Testing the hypothesis is equivalent to testing for significance of \hat{a}_1 .

The success rates for EMM and SMM as well as the overall success rate will be estimated with point estimate and 95% confidence intervals.

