11.4.4 Hypotheses Testing

11.4.4.1 Primary Hypotheses

Hypothesis 2.1: Among Phase 1 treatment failures on stabilizing BUP/NX treatment, those who received EMM will have higher substantial improvement rate than those who received SMM.

The following model will be used to test this hypothesis:

(1)

$$(2) \quad \text{logit}(Y_{ij}) = \beta_0 + \beta_1 \text{txt}_{ij}$$

Here Y_{ij} is a dichotomous measure indicating whether the j^{th} patient of the i^{th} site meets the criteria for Phase 2 ‘continuous substantial improvement’ or not, with $Y_{ij}=1$ for substantial improvement and $Y_{ij}=0$ for no substantial improvement; txt_{ij} is an indicator variable for treatments, with $\text{txt}_{ij}=1$ for EMM group and $\text{txt}_{ij}=0$ for SMM group. The model parameters will be estimated by GEE (see 13.2.7). Testing this hypothesis is equivalent to testing for significance of \hat{a}_1 .

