11.5.4 Projected Number of Sites and Participants Per Site

Based on the simulation results, given the total sample size of 648, variation in the number of site from five to 20 only affects power slightly. Thus, the projected number of sites and patients per site are based on how many sites are willing to join the study and how many patients each site can recruit. It is assumed that 12 sites will enroll in our study, and each site will be able to recruit 54 patients.

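### Both primary tests rest on GEE clustered on 12 sites with no test or variance named: an uncorrected robust Wald test would run near 9% type I error, while the score test would miss the stated power

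*Protocol*

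**What the plan says.** Section 11.2.1 sets the error rate: "All hypotheses will be tested by two-sided tests with level of significance" 0.05. Section 11.2.7 fixes the method: "To account for these correlations in the analysis, all tests will be based on Generalized Estimating Equations (GEE) models". The same section leaves site main effects and site-by-treatment interaction to exploratory analysis, so site enters the primary model only as the cluster. Section 5.2.1 gives the number of clusters: "It is estimated that 12 CTP sites will participate in this study".

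The primary model in both phases is a logit with an intercept and a treatment term. For Phase 1 (section 11.3.4), "The model parameters will be estimated by GEE", and 95% intervals are promised for the success rates in each arm and overall, with no method given. For Phase 2 (section 11.4.4.1), "Testing this hypothesis is equivalent to testing for significance of" the treatment coefficient. Neither section mentions Wald or score, empirical or model-based variance, working correlation, or reference distribution.

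The only test statistic named is in section 11.5.3. There the power analysis uses a GEE quasi-score statistic, referred to chi-square with 1 df.

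Section 11.2.4 says GEE "provides robust inference with respect to misspecification of the covariance" and that "PROC GENMOD in SAS (2003) will be used to carry out these analyses", but both statements follow its description of the quantitative outcomes and weekly urines.

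**The concern.** A cluster-robust variance is estimated from as many independent units as there are clusters, here 12, however many patients are enrolled. Uncorrected, it is biased low, and comparing the Wald ratio with a normal distribution ignores the variance's own uncertainty. Randomising within site does not cure this, because the variance is still built from 12 site-level contributions.

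The robust score test errs in the other direction: it is slightly conservative and loses power. So under either robust reading, one of the two operating characteristics that the protocol states (5% error or at least 80% power) is not met. Both primary hypotheses are affected.

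**Working it through.** **Inputs.** Two-sided 0.05 (11.2.1); 12 sites (5.2.1); Phase 1 n=648, 54 per site (11.3.3.2, 11.5.4); Phase 2 n=324, 27 per site (11.4.3.2, 11.5.3); randomisation within site (11.3.3.1, 11.4.3.1); Phase 1 rates of 10–20% SMM and 20–30% EMM, with within-site correlation 0 to 0.1 (11.5.2); Phase 2 SMM rate 30–50%, correlation about 0.1 (11.5.3).

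**1. The plan's own power.** Power = Φ([d√n − 1.96√(2p̄(1−p̄))] / √(p₀(1−p₀)+p₁(1−p₁))), with n per arm.
- Phase 1, 20% vs 30%, n=324: (1.800 − 1.200)/0.608 = 0.986, so 83.8%; Table 11.1 states 84%. Fourteen of its 15 rows reproduce this way.
- Phase 2, SMM 30%, odds ratio 1.9: p₁ = 0.814/1.814 = 0.449. With n=162: (1.894 − 1.341)/0.676 = 0.817, so 79.3%. With correlation 0.1 and randomisation within site, the effective n is 162/(1−0.1) = 180, giving 83.4%. Section 11.5.3 states at least 80%.

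These figures assume a large-sample test. They make no allowance for there being only 12 clusters.

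**2. Closed-form approximation with 12 equal clusters.**
- Robust Wald z: the uncorrected sandwich is on average 11/12 of the unbiased variance, so the ratio behaves as t₁₁ × √(12/11). P(|t₁₁| > 1.96 × √(11/12)) = P(|t₁₁| > 1.877) = 0.087.
- Robust score: T = 12t²/(11+t²). T > 3.84 requires t² > 3.84×11/(12−3.84) = 5.18, and P(|t₁₁| > 2.28) = 0.044.
- Power for a test designed at 80%, using the t₁₁ critical value 2.20: Φ(2.80 − 2.20) = 0.73.

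**3. Simulation.** 12 sites, beta-binomial site effect common to both arms, equal allocation within site. Main runs used 100,000 replicates per setting with independence GEE: coefficient = difference of pooled logits; sandwich variance = sum over sites of squared site contributions. The exchangeable rows used 2,500 replicates per setting.

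| Test | Type I error | Power Phase 1, 20% vs 30% | Power Phase 2, OR 1.9, SMM 30% |
|---|---|---|---|
| Sandwich Wald z, Phase 1 | 8.4–10.5% | not valid at 5% | – |
| Sandwich Wald z, Phase 2 | 8.5–8.9% | – | not valid at 5% |
| Sandwich Wald z, unequal sites | 9.5–10.3% | – | – |
| Sandwich Wald z, exchangeable | 8.4–9.9% | – | – |
| Generalised score | 4.0–4.5% | 74–79% | 70–74% |
| Sandwich × 12/11 with t₁₁ | 4.7–5.5% in most settings | 76–80% | 71–76% |
| Model-based, exchangeable | 4.6–5.2% | – | – |
| Mantel-Haenszel by site | 4.9–5.2% | 84–87% | 79–83% |

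The corrected sandwich reaches 6.4% at a 10% rate with correlation 0.1, and 5.6–6.2% with unequal sites. Less favourable settings, such as unequal sites, take the lower ends of score-test power to about 72% (Phase 1) and 65% (Phase 2). For the t₁₁ test the lower ends fall to about 75% and 67%.

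**4. Intervals.** With the uncorrected sandwich and a normal reference, nominal 95% intervals cover 90.5–91.5% for the odds ratio and 91.1–92.1% for the SMM arm rate. The corrected version restores 94.4–95.2% for the odds ratio.

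**The case against.** A reader might infer that the planned test has a 9% false-positive rate. The protocol does not support that as a plain statement. It never says Wald and never says sandwich variance for the primary hypotheses. Its one named statistic is the quasi-score, which is conservative here, and model-based errors with exchangeable correlation would hold 5%. Section 11.2.7 claims robustness only for the parameter estimates in the mean model, which is correct. The robust-inference and PROC GENMOD sentences in section 11.2.4 concern other outcomes and do not fix the primary tests. All of this stands, so the inflation is conditional.

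A reader might also take section 11.5.4, where "variation in the number of site from five to 20 only affects power slightly", as accepting five sites for inference. It speaks of power only, and 12 sites are planned.

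The remaining defence is that variance and reference distribution belong in the SAP. That answers only part of the point. The protocol itself commits all tests to site-clustered GEE and states the power. A SAP that chose the score test or a small-sample correction would protect the error rate, but the stated power would no longer hold.

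Finally, stratifying by site departs from the choice in sections 11.2.6 and 11.2.7 to leave the primary analysis unadjusted. That is a real change of estimand, and the sponsor may prefer to keep GEE and restate the power.

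**Conclusion.** The concern holds in conditional form. With 12 clusters, the unstated choice of test puts the true type I error of both primary hypotheses anywhere from about 4% to about 10%. A robust Wald z test breaks the 5% level (typically 8.5–9%, with intervals covering about 91%). A robust score test keeps the level but gives roughly 65–74% power in Phase 2 and 72–79% in Phase 1, against the stated at least 80% and 84%. Only the model-based exchangeable reading of GEE escapes both, and nothing in the protocol selects it.

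The figures rest on assumptions outside the protocol: a beta-binomial site effect shared by both arms, equal arms within site, and, for the upper Wald and lower power figures, unequal sites or low rates. The closed-form values (8.7% and 4.4%) agree with the simulation.

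**What to change.** Make the primary test in each phase site-stratified, in line with the within-site randomisation: a Mantel-Haenszel test by site, or logistic regression with site as a stratum, with model-based errors. This holds about 5% type I error with power close to the stated figures. Keep GEE as a sensitivity analysis with a bias-corrected variance (Mancl-DeRouen or Kauermann-Carroll) and t on 11 df. Use the same correction for any GEE-based interval, including those for the arm success rates if they come from GEE.

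If GEE stays primary, name the test, the working correlation, the variance and the small-sample method, and restate the power for that choice. With t on 11 df it is about 67–76% for Phase 2 and 75–80% for Phase 1.

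The cost of the stratified test is a change of analysis wording, with no change to data collection or sample size. Its downside is that the odds ratio becomes conditional on site, which the report should say.

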11.3 Phase 1: Initial Treatment Study

11.3.1 Overview

Phase 1 is an initial treatment study for subjects meeting DSM-IV criteria for opioid analgesic dependence who do not require an ongoing opioid treatment for pain. Initial treatment consists of BUP/NX for one month plus a random assignment to SMM or EMM. Participants are followed for two more months and treatment failure is assessed continuously. Phase 1 treatment failures are immediately eligible for treatment in Phase 2, although they can elect to remain in Phase 1 through Week 12 follow-up and can transition to Phase 2 at any time up until the conclusion of Phase 1. The maximum duration of patients in Phase 1 is three months but can be as short as one week.

11.3.2 Outcome Measures and Predictors of Response

11.3.2.1 Primary Outcome Measures

The primary outcome measure is the status of treatment: success or failure. Definition of failure/success: A participant is a *Phase 1 success* if all of the following four criteria are satisfied from Week 3 to the end of Phase 1 (Week 12):

1. Use of opioids on four or fewer days per month (beginning after the end of Week 2) as evidenced by self-report.
2. Urine screen for opioids are never positive on two consecutive weeks (beginning after the end of Week 2).
3. Completion of the 4-week medication regimen and 8-week follow-up period (including Week 6 and Week 8 SMM or EMM booster visits) without participating in other formal substance abuse treatment (e.g., methadone maintenance, drug counseling, etc. Self-help groups such as Narcotics Anonymous and treatment for other issues such as medical or psychiatric problems do not count here).
4. Absence of needle use.
5. Absence of no more than one urine sample after Week 2.

A subject who fails one or more of these four criteria at any time from Week 2 to Week 12 is considered a *Phase 1 failure* and is given the option to make the transition immediately to Phase 2. Failures can elect to remain in Phase 1 through Week 12 follow-up and can make the transition to Phase 2 at any time up until the conclusion of Phase 1.

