Data will be collected weekly during Weeks 1-4 of Phase 1 and Weeks 1-16 of Phase 2. Data will be collected every other week during Weeks 5-12 of Phase 1 and Weeks 17-24 of Phase 2. Participants will provide urine samples at each of these assessments for opiates and other drugs of abuse. Severity of withdrawal symptoms, as assessed by Clinical Opiate Withdrawal Scale (COWS), visual analog scale craving scores, concomitant medications, pain assessments, and adverse event data will also be collected.

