Addiction Severity Index (ASI Lite) Follow-Up														X
RBS (Risk Behavior Survey)	X													
CIDI/Depression & PTSD Diagnosis	X													
Fagerstrom Test for Nicotine Dependence	X													X
TREATMENT PLAN														
BUP/NX Induction		X												
BUP/NX Dosing or Taper ***		X	X	X	X	X								X (if applicable)
Medication Accountability		X	X	X	X	X								X (if applicable)
Standard Medical Management		X	X	X	X	X		X		X				X (if applicable)
Enhanced Medical Management		X	X	2X	2X	2X		X		X				X (if applicable)
VISIT DURATION (minutes)	240	60-90					60-90					30	120	

* If participant is a Phase 1 treatment failure AND eligible for Phase 2 AND elects to participate in Phase 2, the final visit CRFs for Phase 1 (Final Visit column) should be completed and then continue to Table 4.2. If the participant does not elect to transition to Phase 2, the regular visit CRFs should be completed according to visit schedule.

** Permitted window of completion is +/- 7 days of scheduled visit during Weeks 6, 8, 10, and 12.

*** May require additional visits for dose adjustment.

**** Physical exam is omitted if participant is transitioning to Phase 2.

***** Urine drug screen for BUP administered in Weeks 10 and 12.

Table 4.2 Visit Schedule Phase 2 for EMM and SMM: 24 Week Study Period

Assessments	*Final Visit Phase 1 (duplicates last column Table 4.1)	PHASE 2 – 24 Week Study Period																								
		BUP/NX Stabilization												BUP/NX Taper				Follow-Up								
		1a	1b	2	3	4	5	6	7	8	9	10	11	12	13	14	15	16	17	18	19	20	21	22	23	24
WEEK NUMBER >>																										
PERMITTED WINDOW >>		+/- 4 days	+/- 3 days of scheduled visit																	**		**		**		**
SCREENING ASSESSMENTS																										
Consent Review		X																								
Eligibility Review		X																								
Randomization		X																								
SAFETY ASSESSMENTS																										
Vital Signs	X	X	X	X	X	X	X	X	X	X	X	X	X	X	X	X	X	X	X	X	X	X	X	X	X	
Lab Tests (LFTs, Chemistry, Hematology, Urinalysis)	X																X									
Pregnancy Test	X					X							X				X									
Adverse Event (AE) Evaluation	X	X	X	X	X	X	X	X	X	X	X	X	X	X	X	X	X	X	X	X	X	X	X	X	X	
Serious Adverse Event (SAE) Evaluation		<<Completed when necessary>>																								
Physical Exam	X																									
Clinical Opiate Withdrawal Scale (COWS)	X	X	X	X	X	X	X	X	X	X	X	X	X	X	X	X	X	X	X	X	X	X	X	X	X	

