6.1 Primary Outcome Measures

The **primary outcome measure** for **Phase 1** will be binary; i.e., “success” or “failure.”

6.1.1 “Success” in Phase 1

“Success” in Phase 1 will be defined as follows: a participant is a “success” if all of the following criteria are satisfied during the 4-week treatment with taper and eight weeks of follow-up:

1. Use of opioids on four or fewer days per month (beginning after the end of Week 2) as evidenced by self-report.
2. Urine screen for opioids are never positive on two consecutive weeks (beginning after the end of Week 2).
3. Completion of the 4-week medication regimen and 8-week follow-up period (including Week 6 and Week 8 SMM or EMM booster visits) without participating in other formal substance abuse treatment (e.g., methadone maintenance, drug counseling, etc.). Self-help groups such as Narcotics Anonymous and treatment for other issues such as medical or psychiatric problems do not count here.
4. Absence of needle use.
5. Absence of no more than one urine sample (beginning after the end of Week 2).

6.1.2 “Failure” in Phase 1

Participants who fail one or more of the criteria for “success” will be considered Phase 1 “failures.”

6.1.3 “Substantial Improvement” in Phase 2

The primary outcome measure for **Phase 2** is “substantial improvement,” defined as abstaining from opioids during the last week AND for at least two of the previous three weeks of the third month of BUP/NX treatment. Abstinence is determined by self-reports of opioid abstinence (missing urines will be considered positive for opioids).

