7.5 Follow-Up

Follow-up is scheduled every other week for all participants for eight weeks following completion of the taper in Phases 1 and 2 (although a participant can end Phase 1 and enter Phase 2 before the eight weeks of Phase 1 follow-up have been completed, if the participant meets failure criteria). The standard procedure for follow-up visits is a face-to-face assessment completed at the study site. However, in limited circumstances as defined by the Operations Manual, sites can collect limited research and safety data by telephone, provided the participant has not withdrawn consent.

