10.2.3 Efficacy Assessments

10.2.3.1 Urine Drug Testing

Urine samples will be collected and analyzed for drugs of abuse prior to dispensing medication. All urine specimens will be analyzed by staff using drug test cups with temperature-controlled monitoring. These cups will be provided by a central supplier to all study sites. OxyImmunoassay and drug screen cards will be used to identify the following substances: oxycodone, benzodiazepines, THC, methadone, cocaine, amphetamine, methamphetamine, propoxyphene, and the Opiate 300 group analytes (morphine, heroin, and codeine). Other drugs may be detected by these analytes at high concentrations. For example, hydrocodone may be detected under the oxycodone test at high concentration levels. The cards will be provided to all study sites from a central supplier.

Urine will be collected at baseline just prior to BUP/NX induction, at each of the weekly visits thereafter, and at each follow-up visit. Urine screens for BUP will be available at Weeks 10 and 12 in Phase 1 and Weeks 22 and 24 in Phase 2. The urine screens for BUP will be used to monitor whether participants defined as "successes" at the end of Phase 1 and "substantially improved" at the end of Phase 2 (in both instances, when they are supposed to be off buprenorphine) are, in fact, taking buprenorphine that they have obtained outside the study.

The results will be recorded on the appropriate CRF.

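### Phase 1 success tests for positive urines on consecutive weeks, but urines are every other week after Week 4, so as scheduled only the Week 3-4 pair can count

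*Protocol*

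**What the plan says.** The Phase 1 primary outcome is success or failure, and success requires every listed criterion to hold. Criterion 2 in Protocol 11.3.2.1 reads "Urine screen for opioids are never positive on two consecutive weeks (beginning after the end of Week 2". The same rule stands in 1.2.1.3, 1.4.4, 4.1.1.2 and 6.1.1. A participant is a success "if all of the following criteria are satisfied during the 4-week treatment with taper and eight weeks of follow-up" (6.1.1), and 11.3.2.1 gives the span as Week 3 to Week 12.

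The sampling schedule is set elsewhere:

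- Section 1.2.2.4: "Data will be collected every other week during Weeks 5-12 of Phase 1 and Weeks 17-24 of Phase 2", and "Participants will provide urine samples at each of these assessments for opiates and other drugs of abuse".
- Section 10.2.3.1: "Urine will be collected at baseline just prior to BUP/NX induction, at each of the weekly visits thereafter, and at each follow-up visit".
- Section 7.5: "Follow-up is scheduled every other week for all participants for eight weeks following completion of the taper in Phases 1 and 2".
- Table 4.1 marks urine screens at Weeks 3, 4, 6, 8, 10 and 12 after Week 2. Its footnote adds: "Permitted window of completion is +/- 7 days of scheduled visit during Weeks 6, 8, 10, and 12".

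Two neighbouring criteria matter here. Criterion 1 allows up to four days of opioid use per month and rests on self-report alone. Criterion 5, with 11.3.3.3, allows one missing urine and makes two or more a failure.

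**The concern.** A rule framed in weeks is applied to a schedule that stops being weekly after Week 4. On the planned dates no follow-up urine has a neighbour in the week before or after it, so positive results in the eight weeks after the taper cannot meet the failure condition. Nothing in the protocol says that consecutive weeks means consecutive tests.

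Urine is the objective measure of opioid use in this definition, and the study is open-label (7.6). If criterion 2 drops out after Week 4, opioid use in follow-up is judged by self-report.

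The definition also works in real time. Failure is assessed continuously (11.3.1), and a participant is invited to Phase 2 on meeting failure criteria (1.4.1.2). The rule therefore decides both how Phase 1 is scored and who is offered the second randomization. Sites could apply it differently, and a rule written later for the analysis cannot restore a Phase 2 offer that was not made.

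**Working it through.** **1. The plan's own figure.** No stated number depends directly on this rule. The nearest, for the same endpoint, is the Table 11.1 power of 84% for 20% against 30% success with n=648. Taking 324 per arm (equal allocation assumed), two-sided 0.05 and a pooled null variance:

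- SE under the null = sqrt(2 × 0.25 × 0.75 / 324) = 0.0340
- SE under the alternative = sqrt((0.20 × 0.80 + 0.30 × 0.70) / 324) = 0.0338
- power = Φ((0.10 − 1.96 × 0.0340) / 0.0338) = Φ(0.986) = 83.8%

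The figure reproduces. It is context only.

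**2. Which pairs can trigger failure, as scheduled.** Sampled weeks after Week 2, from Table 4.1:

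| Successive pair | Gap in weeks | Consecutive weeks? |
|---|---|---|
| 3, 4 | 1 | yes |
| 4, 6 | 2 | no |
| 6, 8 | 2 | no |
| 8, 10 | 2 | no |
| 10, 12 | 2 | no |

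One pair of five qualifies, and none that includes a follow-up urine.

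**3. Result patterns.** Six urines give 2^6 = 64 positive/negative patterns.

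- Literal rule: Weeks 3 and 4 both positive, the other four free: 2^4 = 16 patterns fail.
- Consecutive samples: patterns with no two adjacent positives number 2, 3, 5, 8, 13, 21 for one to six samples, so 64 − 21 = 43 fail.
- The difference is 43 − 16 = 27, and every one of these depends on a follow-up urine.

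These count patterns, not people.

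**4. A sense of scale.** The protocol gives no urine positivity. Assume each test is positive with probability q, independently. The literal rule fails q². The sample-based rule fails 1 − r6, where r0 = r1 = 1 and r(n) = (1 − q) r(n−1) + q(1 − q) r(n−2).

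| Assumed q | Fail criterion 2, literal | Fail criterion 2, consecutive samples |
|---|---|---|
| 10% | 1.0% | 4.6% |
| 20% | 4.0% | 16.4% |
| 30% | 9.0% | 32.7% |
| 50% | 25% | 67.2% |

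These are failures on criterion 2 alone. Some of these participants would also fail another criterion, so the change in the success rate cannot exceed the gap between the columns and would usually be smaller.

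**5. Actual dates instead of scheduled weeks.** Suppose the Week 6 visit is held in Week 7 and the Week 8 visit on time. The two samples are then in consecutive weeks, and two positives mean failure. Held on schedule, the same two results do not.

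To see how often this can arise, take the target as the last day of the study week. The Week 6 visit can fall on 1 day of Week 5, 7 of Week 6 and 7 of Week 7. The Week 8 visit can fall on 1 day of Week 7, 7 of Week 8 and 7 of Week 9. Adjacent-week combinations are 7 × 1 + 7 × 7 = 56 of 15 × 15 = 225, or 25%. The pairs 8-10 and 10-12 give the same, and a first-day target does not change it. For Weeks 4 and 6 the share is 25/105 to 28/105, or 24-27%. Weighting all permitted days equally is an assumption.

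**The case against.** The strongest reply is that a sensible reader takes consecutive weeks to mean consecutive sampled weeks. All five pairs then count and the criterion works. That may be the intent, but all five statements say weeks and none defines the term for alternate-week visits. If it is the intent, the correction below is the wording it needs.

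A reader might infer that no follow-up urine can ever cause failure. The documents do not support that. The 7-day window can put follow-up samples in adjacent calendar weeks, and two missing urines cause failure under criterion 5, in follow-up as well. The first of these does not rescue the rule, because it makes the outcome depend on whether a visit ran early or late.

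A reader might also infer that success in follow-up rests on self-report alone, or that someone who denies relapse is shut out of Phase 2. Both go too far. Criterion 3 requires completion, including the Week 6 and 8 booster visits, without other formal treatment. Criterion 4 excludes needle use. Dropouts before Week 12 are failures and are eligible for Phase 2 (11.3.3.3). Urine results are reviewed at medical management visits (8.2.1), and admitting relapse opens a further 12 weeks of BUP/NX, which works against denial. What stands is narrower: as scheduled, positive opioid results after Week 4 carry no weight.

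**Conclusion.** The point holds in this form: as scheduled, criterion 2 can be met only by the Week 3 and Week 4 urines. Followed literally, it therefore gives a wrong result for a participant positive at Weeks 6, 8, 10 and 12 who reports four or fewer use days per month and meets the other criteria. If actual dates are used, it gives inconsistent results. This needs no assumption beyond the printed schedule and window. It affects the Phase 1 primary endpoint and entry to Phase 2, so it should be settled in the protocol.

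The number of participants affected is unknown. It might be tempting to turn the defect into a loss of power or an inflated false-positive rate. That needs a denial rate, and for false positives a difference in denial between arms, and the protocol gives neither. It would also have to leave out those who fail anyway: about 30% treatment dropout is expected in Phase 1 (11.4.3.2), and anyone who discontinues the study before Week 12 is a failure. No such figure is offered here.

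Nor does the point extend to buprenorphine urines. Section 10.2.3.1 says "Urine screens for BUP will be available at Weeks 10 and 12 in Phase 1 and Weeks 22 and 24 in Phase 2" and describes them as a check on outside buprenorphine use. Making them part of the endpoint would be a separate decision.

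**What to change.** In 1.2.1.3, 1.4.4, 4.1.1.2, 6.1.1 and 11.3.2.1, replace the reference to two consecutive weeks with: *two consecutive scheduled urine samples (Weeks 3, 4, 6, 8, 10, 12), regardless of actual visit date within the window*.

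State how a single missing sample between two others is handled: either it breaks the run, or positives on both sides of it count as consecutive. Either agrees with 11.3.3.3, under which one missing urine does not by itself prevent success. Coding the missing sample as positive would sit badly with that section.

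The cost is wording only, with no new samples or visits. There are two consequences:

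- The rule becomes stricter. Two positives two weeks apart can come from isolated days of use that criterion 1 tolerates, and the sponsor should confirm that this is wanted.
- The Phase 1 success rate will fall and Phase 2 eligibility will rise, by an amount that depends on follow-up urine positivity. The 20% success and 50% transition assumptions in 11.5.1 should be rechecked. Table 11.1 shows why the size matters: starting from 20% against 30% (84% power), a move to 15% against 25% gives 89%, but 15% against 23% gives 74%.
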